14.0 STATISTICAL CONSIDERATION

14.1 Study design

FC-9 is a single arm, study using the combination of durvalumab and tremelimumab for 4 cycles followed by durvalumab as monotherapy cycles 5 through 24 (1 cycle = 28 days). Study therapy will be initiated following 3 doses of palliative hypofractionated radiation on Days -2, -1 and Day 0, prior to beginning Cycle 1.

14.2 Statistical design and sample size analysis

The optimal two-stage design ([Simon 1989](#)) to test the null hypothesis that $ORR_0 \leq 0.05$ versus the alternative that $ORR_A \geq 0.20$ has an expected sample size of 16.14 and a probability of early termination of 0.54. If the combination study therapy is actually not effective, there is a 0.080 probability of concluding that it is (the target for this value was $\alpha = 0.10$). If the combination study therapy is actually effective, there is a 0.197 probability of concluding that it is not (the target for this value was $\beta = 0.20$).

Patients who complete both Cycle 1 and Cycle 2, and undergo the first restaging scan after Cycle 2 for the determination of tumor response will be determined as evaluable. Non-evaluable patients will be replaced.

After testing the study therapy combination on 12 evaluable patients in the first stage, the trial will be terminated if 0 patients respond. If the trial goes on to the second stage, a total of 21 evaluable patients will be studied. If the total number responding is less than or equal to 2, the combination is rejected. If 3 or more responses are observed ($ORR \geq 14.3\%$) after the second stage of the study, the combination will be considered for further study.

14.3 Monitoring

- A medical review team comprising of the Protocol Chair, NSABP Medical Director, study statistician, designated physician(s), and designated DSSM staff will formally monitor the study on a monthly basis to identify accrual, toxicity, and any endpoint problems that might be developing.
- During the trial, the protocol officer, and designated DSSM staff will participate in a weekly Web-ex with investigators who have a patient enrolled on the FC-9 study. Investigators who have a patient receiving study therapy are required to participate. All FC-9 study staff are encouraged to attend.
- The maximum grade for each type of toxicity will be recorded for each patient, and frequency tables will be reviewed to determine toxicity patterns.

15.0 **PUBLICATION INFORMATION**

The publication or citation of study results will be made in accordance with the publication policy of the NSABP that is in effect at the time the information is to be made publicly available.

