8.0 TREATMENT MANAGEMENT

8.1 General instructions

- The NCI CTCAE v4.0 must be used to grade the severity of AEs.
- All treatment decision must be based on the AE requiring the greatest modification.
- Drug doses that have been reduced may not be re-escalated.
- All hematologic, gastrointestinal, and genitourinary toxicities must be < Grade 2 prior to initiating Dose 1 of study therapy. Patients unable to receive Dose 1 will be considered screen failures.

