3.1 Study Period and Visit Window Definitions

3.1.1 Study Periods

The accrual period is expected to be 24 months.

Enrolled patients will receive the combination of tremelimumab (75 mg IV infusion) and durvalumab (1500 mg IV infusion) on Day 1 for 4 cycles. Beginning with Cycle 5 through Cycle 12, patients will receive durvalumab alone (1500 mg/IV infusion) on Day 1 of each 28 day cycle.

All AEs will be recorded from the first dose of study therapy until 90 days after the last dose of study therapy or at the cessation of study therapy if the patient initiates new anti-cancer therapy, whichever is earlier.

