3.3.2 Safety Population

The Safety population will consist of all patients who receive at least one dose of any study medication.

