4.3 In- and Exclusion Criteria

This will not be analyzed since specific criteria are not collected on the eCRF.

5. Demographic and Other Baseline Characteristics

Descriptive statistics with respect to patient characteristics at baseline will be displayed for [the ITT population].

The summary of demographic data and baseline disease characteristics will present the following variables:

- Age, sex, race, and ethnicity
- ECOG performance status (0 to 1)
- Time since initial diagnosis of colon cancer

6. Safety Evaluation

The safety analyses will be presented on the [ITT population].

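### No toxicity event obliges a pause in accrual, and routine safety counting starts only after the SBRT has been given

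*Combined protocol and SAP*

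**What the plan says.** **Review.** Under protocol 14.3 a team that includes the study statistician "will formally monitor the study on a monthly basis to identify accrual, toxicity, and any endpoint problems that might be developing". There is also a weekly web call: "Investigators who have a patient receiving study therapy are required to participate". Toxicity frequency tables are reviewed. Serious adverse events (SAEs), AEs of special interest of Grade 2 or higher, and deaths not due to disease progression go to the coordinating department within 24 hours (10.4, 10.7.2).

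**Trial-level stop.** Protocol 14.2: after 12 evaluable patients "the trial will be terminated if 0 patients respond". SAP 2.2.1 agrees. Evaluable means Cycles 1 and 2 completed and the first restaging scan done. "Non-evaluable patients will be replaced", and no maximum number treated is given.

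**When safety counting starts.** Routine AE recording begins with the first dose of study therapy (10.8; SAP 3.1.1). Sections 7.0 and 14.1 place SBRT before study therapy. Section 8.1 adds: "Patients unable to receive Dose 1 will be considered screen failures".

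**Who is counted.** The Safety population in SAP 3.3.2 is "all patients who receive at least one dose of any study medication". SAP section 6 states, with the population in square brackets, "The safety analyses will be presented on the [ITT population". SAP 3.3.1 defines that population as the evaluable patients. SAP Appendix 1, however, assigns every AE and death table to Safety.

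**The concern.** The regimen under test is SBRT followed by two checkpoint inhibitors, and its safety is a stated secondary aim (3.2.3). There is no control arm. For the three-part combination, section 2.8 cites mouse experiments. The 22-patient human trial of SBRT plus an anti-CTLA4 antibody in 2.7.1 is summarised for response and survival, without a toxicity rate. Section 8.6.1 itself warns that SBRT may make delayed, partly immune-mediated toxicity more frequent or more severe.

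In that setting two things stand out. Even a treatment-related death requires no recorded decision before the next patient is entered. And the counting rules are written around the drugs, although radiation is the first component delivered. A patient made too unwell by SBRT to start the drugs is the patient whose experience matters for a safety claim about the regimen, and the current definitions leave that patient out of the safety tables.

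**Working it through.** **1. The existing stop depends on response alone.** Inputs from 14.2: 12 then 21 evaluable, stop at 0 of 12, reject at 2 or fewer of 21.

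- Early termination at a 5% response rate: 0.95^12 = 0.5404 (plan: 0.54).
- Expected size: 12 + (1 − 0.5404) × 9 = 16.14 (plan: 16.14).
- Exact two-stage enumeration: type I error 0.0804 at 5%, type II error 0.1967 at 20% (plan: 0.080 and 0.197).

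The figures reproduce, and no toxicity term enters them.

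**2. Other toxicity rules.** Section 8.2.2 and Table 7 hold, reduce or stop treatment for one patient. Section 10 governs reporting. Neither is tied to accrual.

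**3. Pace.** SAP 3.1.1: "The accrual period is expected to be 24 months".

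- With no losses: 21/24 = 0.875 patients per month.
- At an assumed 20% non-evaluable: 21/0.80 = 26.25 treated, and 26.25/24 = 1.09 per month.
- Patients inside an 8-week window: 0.875 × 56/30.44 = 1.6, or 1.09 × 56/30.44 = 2.0.

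Monthly review thus meets about once per new patient.

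**4. What is captured, by period.**

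| Event | Days -2 to 0 | From first drug dose |
|---|---|---|
| SAE related to a protocol procedure | Yes, from consent (10.7.1) | Yes |
| SAE regardless of relationship | No (10.7.1) | Yes |
| Non-serious AE on Form AE | No (10.8; SAP 3.1.1) | Yes |
| Counted as treatment-emergent | No (SAP 6.2) | Yes |
| Patient in Safety population | Only if a drug dose follows, when study medication means drugs (SAP 3.3.2) | Yes |

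Table 2 already schedules an AE assessment within 72 hours before Day 1 of Cycle 1, which overlaps the SBRT days. The visit exists; the recording rule omits what it may find.

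**5. Size of a related-death trigger.** With q the true related-death rate (assumed; the documents give none for this regimen) and patients independent, P(at least one by n treated) = 1 − (1 − q)^n. I use n = 24 because 21 evaluable needs 21/0.90 = 23.3 treated at an assumed 10% loss, and n = 12 for a trial ending at Stage I.

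| q | n = 12 | n = 24 |
|---|---|---|
| 0.5% | 5.8% | 11% |
| 1% | 11% | 21% |
| 2% | 22% | 38% |
| 5% | 46% | 71% |

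**6. Why a Grade 3 or higher count is only optional.** As an illustration, pause at 5/6, 8/12, 11/18 or 14/24 treated with a related Grade 3 or higher event, for a 40% acceptable rate. Exact sequential binomial gives a pause with probability 0.118 at a true 40% and 0.726 at 60%. If the acceptable 8-week rate were really 20%, the same boundary would catch a doubling to 40% only 0.118 of the time. A boundary set for 20% (4/6, 5/12, 7/18, 9/24) gives 0.102 at 20% and 0.763 at 40%.

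All these figures assume that every patient is observed for the full 8 weeks. If 20% of patients were observed for half the window with events spread evenly (assumed), the observed rate is multiplied by 0.80 + 0.20 × 0.5 = 0.90. Detection of the 20-point excess then falls from 0.726 to 0.517 for the 40% boundary, and from 0.763 to 0.633 for the 20% boundary.

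**The case against.** The strongest reply is that a small single-arm trial entering about one patient a month, with monthly review, a compulsory weekly call and 24-hour reporting, already has closer oversight than most written rules would add. Qualifying reports also go to the FDA and the manufacturer, and investigators report to their review boards (10.7.2). The team can halt the trial whenever it judges that necessary. This stands, and it limits the point to a modest improvement.

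A reader might infer four stronger things that the documents do not support.

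- *That toxicity is unmonitored.* Section 14.3 and section 10 show otherwise.
- *That SBRT toxicity is lost altogether.* Under 10.7.1, SAEs related to protocol-mandated procedures are recorded from consent. The main gap is in non-serious events and in the analysis population.
- *That replacement hides toxicity.* Replaced patients leave the response count, but anyone who received a drug dose stays in the Safety population. The conflicting text in SAP section 6 is a bracketed entry in a SAP marked draft, and its own table list says Safety.
- *That a Grade 3 or higher boundary is required.* The only reference rate, 41/102 (40%) in section 2.5, comes from lung cancer without SBRT, is pooled over doses and has no stated time window. Table 7 lets patients resume after several kinds of Grade 3 event, and 8.6.2 expects transient liver-enzyme rises after SBRT. Collection also stops when new therapy starts (10.8). The choice of boundary belongs to the sponsor.

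It is also fair to say that moving the start of AE recording touches several sections, so it is more than a one-line edit.

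**Conclusion.** The point holds in a limited form. Oversight is in place. What is missing is an event that obliges a documented decision, together with complete counting of toxicity from the first component of the regimen.

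The related-death trigger would rarely fire if such deaths are very uncommon, and would fire in most trials at a 5% rate. That rests on assumed rates, independence between patients and 24 treated; if the trial ends at Stage I the chances are roughly half to two thirds as large. The counting gap covers about three days per patient, plus every irradiated patient who never starts the drugs. The documents give no figure for how many that will be, so its numerical effect cannot be stated. The exclusion from the Safety population assumes that study medication means the two drugs, which fits the protocol's use of study therapy but is not spelled out in the SAP.

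Neither gap affects the response analysis or its error rates.

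**What to change.** 1. **Protocol 14.3.** State that accrual pauses after any death judged related to study therapy or SBRT until the existing medical review team records a decision to continue, modify or stop. The report that sets this off is already required (10.4.2), and no new committee is needed.
2. **Recording and analysis.** Start AE recording at the first SBRT fraction. Define the Safety population as all patients with at least one SBRT fraction or drug dose, and present the SAP section 6 safety analyses on it. Keep irradiated patients who cannot receive Dose 1 in that population and set a short AE follow-up for them, for example the 30-day visit in Table 2. Make matching edits to protocol 8.1, 10.7.1 and 10.8, and to SAP 3.1.1, 3.3.2, 6 and 6.2 (including the treatment-emergent definition).

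**Cost.** Possibly a short pause after a single death, even when the underlying rate is acceptable (21% by 24 treated at a 1% rate). A few days of extra non-serious AE data per patient. Brief follow-up of the irradiated patients who receive no drug. Patient-level dose rules do not change.

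**Optional.** A Grade 3 or higher count boundary, once the sponsor fixes an acceptable 8-week rate, and a maximum number treated. Any operating characteristics printed for the boundary should say that they assume full 8-week observation of every patient.

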0	Fully active; able to carry on all pre-disease performance without restriction	90–100%
1	Restricted in physically strenuous activity but ambulatory	70–80%
2	Ambulatory and capable of self-care, but unable to carry out any work activities	50–60%
3	Capable of only limited self-care; confined to bed or chair more than 50% of waking hours	30–40%
4	Completely disabled	10–20%

NCI DEFINITION FOR ACTIVITIES OF DAILY LIVING

Activities of daily living (ADL) are the tasks of everyday life. These activities include:

- eating
- dressing
- getting into or out of bed or chair
- taking a bath or shower
- using the toilet

APPENDIX B

HYPOFRACTIONATED RADIATION THERAPY GUIDELINES

The lesion selected for radiation should be a lesion that can be safely radiated with focal irradiation (SBRT) for which radiation at the limited, palliative doses contemplated would be considered medically appropriate and in accord with acceptable radiation oncology practice. Appendix B offers guidance for this study.

1.0 Dose Specification

1.1 *Hypofractionated SBRT*

Stereotactic Body Radiation Therapy (SBRT) is the treatment modality utilized for this protocol. Here, stereotactic refers to the targeting, planning, and direction of radiation treatment along any trajectory towards a well-defined and visualized 3-D target. The exact coordinates of this 3D target is what differentiates it from conventional radiation therapy where skin or bony landmarks serve as tumor surrogates. This treatment will require 3-dimensional targeting of the tumor either by fiducial placement or by target visualization using a pre-treatment cone-beam CT (CBCT).

1.2 *Dose fractionation*

All patients will be treated to a single target with a total dose of 27.0 Gy delivered at 9.0 Gy per fraction on three consecutive days with a minimum of 18 hours between treatments required.

1.3 *Target lesion*

A single target lesion identified within the lung or liver will be treated with SBRT as a component of this study. The target lesion should be $\leq 100 \text{ cm}^3$.

1.4 *Premedications*

Analgesic premedication to avoid general discomfort during long treatment duration is recommended when appropriate. Anti-emetics (e.g., Compazine) should be prescribed for those where the 50% isodose line approaches the stomach or bowel. Pretreatment with corticosteroids (e.g., dexamethasone) is not recommended.

2.0 Technical Factors

2.1 *Physical factors*

Only 6 mV photons (x-ray) beams produced by a linear accelerator is allowed for this protocol.

2.2 *Treatment platforms*

This trial allows for commercially available photon producing treatment units equipped with a linear accelerator with image (or fiducial) guidance (e.g. Cyberknife, TrueBeam, Trilogy).

3.0 Localization, Simulations, and immobilization

3.1 *Patient positioning*

Patients will be positioned in a stable, reproducible position using either a vac bag or thermoplastic mask (lung lesions above the carina) immobilization device. The treatment position should be reproducible from treatment to treatment.

APPENDIX B (continued)

3.2 *Internal organ motion*

Special considerations must be made to account for the effect of internal organ motion on target positioning and reproducibility. For the purpose of this protocol, accelerator beam gating with the respiratory cycle using the RPM respiratory motion management system is the preferred approach. For those patients treated on the Cyberknife treatment platform, fiducial tracking is also acceptable. Respiratory gating (or tracking) must be reliable enough to insure that the GTV motion is accounted if motion is greater than 0.5 cm.

3.3 *Localization*

Isocenter localization images should be obtained on the treatment unit immediately before treatment to ensure proper alignment of the simulated fields. These IGRT images can be obtained with planar kV imaging devices. For the Cyberknife system agreement between the treatment unit isocenter or reference point in space must be checked for agreement with the imaging isocenter prior to treatment. For lesions where respiratory gating is utilized, fluoroscopy should be used to confirm the appropriate gating window.

4.0 **Treatment Planning and Target Volumes**

4.1 *Patient simulation and image acquisition*

Computed tomography is the primary image platform for targeting and treatment planning. The planning CT scans must allow simultaneous view of the patient anatomy and fiducial placement if necessary. Intravenous (I.V) contrast during the planning CT is optional but recommended but can be avoided if a diagnostic CT with contrast was obtained to delineate the tumor and organs at risk within 8 weeks of simulation is available. Image slice thickness should be 1.25 mm per slice.

The target lesion will be outlined by an appropriately trained physician and designated the gross tumor volume (GTV). The target will be drawn using CT with appropriate windowing for the target (lung – pulmonary windows, liver – hepatic windows); however, additional diagnostic images can be fused to assist in target delineation. This includes FDG-PET as well as MRI which is the preferred modality for liver lesions. The target lesion for this study is limited to a GTV volume $\leq 100 \text{ cm}^3$.

Planning target volume (PTV) generation will be created following the motion management simulation (i.e., 4D CT). Here, the physician will delineate the primary target and with the assistance of physics support analyze the phases of the respiratory cycle and associated movement in relationship to the tumor in its most superior extent. Respiratory gating should be utilized for tumors with excursion greater than 0.5 cm. A minimum of 0.3-0.5 cm should be added to the movement determined on the motion assessment to generate the PTV.

4.2 *Dosimetry*

Three-dimensional coplanar or non-coplanar beam arrangements will be custom designed for each dose to deliver highly conformal prescription dose distributions. Non-opposing, non-coplanar beams are preferred. Typically > 10 beams will be used with roughly equal weighting. Generally, more beams are used for larger lesions. When static beams are used, a minimum of 7 non-opposing beams should be used.

For arc rotation techniques, a minimum of 340 degrees (cumulative for all beams) should be utilized. In order to obtain acceptable coverage, field aperture size and shape should

APPENDIX B (continued)

correspond nearly identically to the projection of the PTV along a beam's eye view (i.e., no additional "margin" for dose buildup at the edges of the blocks or MLC jaws beyond the PTV). The only exception should be when observing the minimum field dimension of 3.5 cm when treating small lesions.

As such, prescription lines covering the PTV will typically be the 60-90% line (where the maximum dose is 100%); however, higher isodoses (hotspots) must be manipulated to occur within the target and not in adjacent normal tissue. The treatment isocenter or setup point in stereotactic coordinates will be determined from system fiducials (and can be adjusted pre-treatment depending on the results from localization imaging studies) and translated to the treatment record.

Prescription Dose Constraints for Treatment Planning

- **Maximum dose:** The treatment plan should be created such that 100% corresponds to the maximum dose delivered to the patient. This point must exist within the PTV.
- **Prescription isodose:** The prescription isodose surface must be > 80% and < 90% of the maximum dose.
- **Prescription Isodose Surface Coverage:** The prescription isodose surface will be chose such that 95% of the PTV is conformally covered by the prescription isodose surface and 99% of the PTV receives a minimum of 90% of the prescription dose.
- **High Dose Spillage:** The cumulative volume of all tissue outside the PTV receiving a dose > 105% of the prescription dose should be no more than 15% of the PTV volume.
- Conformality of PTV coverage will be judged such that the ratio of the volume of the prescription isodose to PTV is ideally < 1.2.

5.0 Critical structures

5.1 *Pulmonary lesions*

- **Skin:** A skin contour should be created for all patients. This will be equal to the body contour minus 3 mm. The maximum dose should be less than the prescription dose (i.e., < 27 Gy).
- **Lung:** Both lungs minus the PTV should be contoured as part of the study. The dose tolerance is below that of the prescription dose. Conformality as described above including conformality index should be achieved.
- **Carina and bronchial tree:** The distal 2 cm of the trachea, the carina, the right and left mainstem bronchi, the right and left upper lobe bronchi, the intermedium bronchus, the right middle lobe bronchus, the lingular bronchus, and the right and left lower lobe bronchi should be contoured. The dose to this structure should be less than the prescription dose (i.e. < 27.0 Gy).
- **Esophagus:** Max dose < 27.0 Gy.

APPENDIX B (continued)

5.2 *Liver lesions*

- Skin: See above.
- Liver: The entire liver should be contoured. As with the lung, the conformality index should be achieved for target coverage. The GTV should be limited to $\leq 100 \text{ cm}^3$. For the liver $V_{12} < 700 \text{ cc}$.
- Stomach or Bowel should be contoured 2 cm above and below the target. The maximum dose should be less than the prescription dose (i.e. $< 27 \text{ Gy}$).

APPENDIX C CONTRACEPTION

Female patient of child-bearing potential

- Females of childbearing potential are defined as those who are not surgically sterile (i.e., bilateral tubal ligation, bilateral oophorectomy, or complete hysterectomy) or post-menopausal.
 - Women will be considered post-menopausal if they have been amenorrheic for 12 months without an alternative medical cause. The following age-specific requirements apply:
 - Women <50 years of age would be considered post-menopausal if they have been amenorrheic for 12 months or more following cessation of exogenous hormonal treatments and if they have luteinizing hormone and follicle-stimulating hormone levels in the post-menopausal range for the institution or underwent surgical sterilization (bilateral oophorectomy or hysterectomy).
 - Women ≥50 years of age would be considered post-menopausal if they have been amenorrheic for 12 months or more following cessation of all exogenous hormonal treatments, had radiation-induced menopause with last menses >1 year ago, had chemotherapy-induced menopause with last menses >1 year ago, or underwent surgical sterilization (bilateral oophorectomy, bilateral salpingectomy or hysterectomy).
- Females of childbearing potential who are sexually active with a non-sterilized male partner must use at least 1 **highly** effective method of contraception ([Table 9](#)) from the time of screening and must agree to continue using such precautions for 6 months after the last dose of durvalumab and tremelimumab combination therapy and for an additional 3 months after the last dose of durvalumab monotherapy. Non-sterilized male partners of a female patient must use male condom plus spermicide throughout this period. Cessation of birth control after this point should be discussed with a responsible physician.
- Not engaging in sexual activity for the total duration of the drug treatment and the drug washout period is an acceptable practice; however, periodic abstinence, the rhythm method, and the withdrawal method are not acceptable methods of birth control. Female patients should also refrain from breastfeeding throughout this period.

Male patients with a female partner of childbearing potential

- Non-sterilized males who are sexually active with a female partner of childbearing potential must use a male condom plus spermicide from screening through 6 months after receipt of the final dose of durvalumab and tremelimumab combination therapy and for an additional 3 months after receipt of the final dose of durvalumab monotherapy.
- Not engaging in sexual activity is an acceptable practice; however, occasional abstinence, the rhythm method, and the withdrawal method are not acceptable methods of contraception.
- Male patients should refrain from sperm donation throughout this period.
- Female partners (of childbearing potential) of male patients must also use a highly effective method of contraception throughout this period ([Table 9](#)).

Highly effective methods of contraception

Highly effective methods of contraception defined as one that results in a low failure rate (i.e., less than 1% per year) when used consistently and correctly are described in [Table 9](#). *Note:* Some contraception methods are **not** considered highly effective (e.g., male or female condom with or without spermicide; female cap, diaphragm, or sponge with or without spermicide; non-copper containing intrauterine device; progestogen-only oral hormonal contraceptive pills where inhibition of ovulation is not the primary mode of action [excluding Cerazette/desogestrel which is considered highly effective]; and triphasic combined oral contraceptive pills).

Table 9. Highly Effective methods of contraception (<1% failure rate)

Barrier/Intrauterine Methods	Hormonal Methods

- Copper T intrauterine device- Levonorgesterel releasing intrauterine system (e.g., Mirena®)^a	
- Etonogestrel implants: e.g., Implanon or Norplant- Intravaginal device: e.g., ethinylestradiol and etonogestrel- Medroxyprogesterone injection: e.g., Depo-Provera- Normal and low dose combined oral contraceptive pill- Norelgestromin/ethinylestradiol transdermal system- Cerazette (desogestrel)

^aThis is also considered a hormonal method.

Statistical Analysis Plan

SPONSOR:	NSABP
PROTOCOL TITLE:	A Phase II Study of the Dual Immune Checkpoint Blockade with Durvalumab (MEDI4736) plus Tremelimumab Following Palliative Hypofractionated Radiation in Patients with Microsatellite Stable (MSS) Metastatic Colorectal Cancer Progressing on Chemotherapy
STUDY CODE:	NSABP Protocol FC-9
Version	Draft July 06, 2019

For Biostatistics:

Author: [name], Consulting Statistician

For Sponsor:

Reviewer: [name], Project Data Manager

Approver: [name], Clinical Research Physician

Table of Contents

1. INTRODUCTION	3
2. STUDY DESIGN AND OBJECTIVES	3
2.1 Study Objectives.....	3
2.1.1 Co-Primary Objectives	3
2.1.2 Secondary Objectives	3
2.2 Study Design.....	3
2.2.1 Stage I futility analysis	3
2.2.2 Stage II	3
2.3 Sample Size Justification.....	4
3. GENERAL ANALYSIS DEFINITIONS	4
3.1 Study Period and Visit Window Definitions.....	4
3.1.1 Study Periods	4
3.1.2 Entry, Treatment, and Follow-up	4
3.2 Planned Analyses	4
3.2.1 Stage I Analysis	4
3.2.2 Final Analysis.....	5
3.3 Definition of Analysis Populations.....	5
3.3.1 Intent-to-Treat Population (ITT).....	5
3.4 Calculated Variables	5
3.5 Changes to Protocol	5
4. STUDY PATIENTS.....	5
4.1 Disposition of Patients	5
4.2 Protocol Deviations	5
4.3 In- and Exclusion Criteria.....	6
5. DEMOGRAPHIC AND OTHER BASELINE CHARACTERISTICS.....	6
6. SAFETY EVALUATION.....	6
6.1 Extent of Exposure.....	6
6.2 Adverse Events.....	6
6.3 Deaths	7
7. EFFICACY ANALYSIS.....	7
7.1 Primary Analysis of Stage II: Objective Response Rate	7
7.2 Secondary Efficacy Analyses.....	7
7.2.1 Clinical Benefit Rate.....	7
7.2.2 Duration of Response.....	8
8. EXPLORATORY TRANSLATIONAL STUDIES.....	8
9. APPENDICES.....	8
APPENDIX 1: LIST OF STATISTICAL TABLES	9
APPENDIX 3: LIST OF DATA LISTINGS	10

1. Introduction

This Statistical Analysis Plan (SAP) is written for the clinical trial protocol NSABP FC-9, version dated November 7, 2016. The ICH guideline E3 "Structure and Content of Clinical Study Reports" was used as a guide to the writing of the plan.

2. Study Design and Objectives

The FC-9 study is designed as a phase II, open label, single arm study of the dual immune checkpoint blockade with the combination of durvalumab and tremelimumab following hypofractionated palliative radiation in patients with microsatellite stable (MSS) metastatic colorectal cancer (mCRC) who have progressed on chemotherapy.

Study design is a Simon two-stage design (12 patients stage I, 9 patients stage II).

If at least one patient in the first stage have an objective response, the study will proceed to Stage II (*expansion cohort*). The expansion cohort will enroll 9 additional patients. If ≥ 3 patients have objective response, the study therapy will be considered for further testing.

There will be up to 21 evaluable patients (unevaluable patients will be replaced).

